Study Objective(s)	
Our goal for this study is to generate preliminary data that is needed to support an application to NIH for funding of a larger, adequately-powered study to explore whether a set of genotypes, that increase the risk for nonalcoholic fatty liver disease (NAFLD), predispose individuals to increased de novo lipogenesis (DNL) and liver fat accumulation when exposed to fructose intake.
 
Primary Objective: To determine the impact of acute and prolonged exposure of fructose on hepatic lipid accumulation in adolescents and young adults (12-40 years) with high and low genetic risk for NAFLD using liver mass resonance imaging (MRI).
 
Secondary Objective: To explore the genetic-specific effects of fructose on markers of liver fat accumulation (fibroscan⁵ and fatty liver index⁶) and serum biomarkers related to lipids, uric acid and liver function.

Test Article(s) (If Applicable)	Sugar-Sweetened beverages
Study Design	
 a. We will screen 200 Caucasian children and young adults (12-40 years) to obtain 24 children and 24 young adults who are overweight/obese and drink <14 fructose drinks/week to participate in a 3-week fructose intervention study. The 200 participants will be genotyped for 10 SNPs involved in lipid metabolism and associated with increased NAFLD risk in previously published studies^{7,8}. We will select 12 children and young adults with 15 or more risk alleles and 12 children and 12 young adults with 6 or fewer risk alleles and provide them fructose + glucose⁹ drinks who will ingest one drink (equal to 2 soft drinks) per day for 3 weeks; b. We will measure liver fat using Liver MRI^{9,10} and transient elastography (Fibroscan)⁵ at week 0 and 3;

c. Data will be analyzed using paired and unpaired students T test to differentiate the responses between the time points and between the two groups, respectively.

Specific Aim2: Determine the impact of acute exposure of fructose on hepatic *de novo* lipogenesis

- Using the cohort described in Specific Aim1, we will conduct oral fructose tolerance test at week 0 and week 3;
- We will measure liver fat using Fibroscan
- Data will be analyzed using unpaired students T test and repeated measures ANOVA to differentiate the responses between and within the two groups, respectively.

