1.4 Relevant Literature and Data

The studies similar to that being conducted here have been conducted before (Table 1, Figure 1). The only difference is that we are using a set of 10 genotypes instead of individual genotypes that were used in studies before.

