We will conduct a spot glucose check using a glucometer (Accu-Chek, Roche Diagnostics, CH) to check that the glucose levels of the participants are in the normal range (fasting < 100mg/dl, post meal < 140 mg/dl and random < 200 mg/dl). The exclusion criteria includes ages < 12 and > 40 years, known alcohol abuse or fructose intake > 14 drinks per week, not of Caucasian ethnicity, glucose levels > 100 mg/dl if fasting, > 140mg/dl if within 2 hours post meal and > 200 mg/dl if random, and known diagnosis of diabetes, fructose intolerance and chronic kidney disease.

We will collect saliva from the eligible 200 children and young adults, extract DNA and genotype 10 SNPs shown in Table1.

Genotyping: SNPs will be genotyped from DNA extracted from saliva. Genotyping will be conducted in [name] lab using TaqManSNP genotyping assays (Applied Biosystems, Foster City, CA). The minor allele frequencies (MAFs) of these SNPs range between 7 and 49% based on Caucasian ethnic background. Therefore we are confident about finding 48 individuals with all 10 SNPs. If we don't find individuals with the 10 SNPs, we will mine the literature and find more SNPs that have a role in liver lipogenesis.

4.2

Intervention/Treatment procedures (by visits)

Phase2: Selection of 48 participants for the acute fructose challenge and 3-week intervention study:

The risk allele will be defined as the allele that is associated with higher levels of liver lipogenesis or fat as per previously published studies in Caucasians. The number of risk alleles will range from 0 to 20. The SNP will get a score of 2 with two risk alleles, 1 with one risk allele and 0 with no risk alleles. All the score will be added to get a cumulative score between 0 and 20 for 10 SNPs. We will select participants having > 15 risk alleles and < 6 risk alleles for our acute challenge and 3-week intervention study.

Phase 2&3- visit 1- MRI scan: The 48 individuals enrolled will visit the UNC NRI clinical suite run by the Human Research Core. After obtaining consent, they will be taken to the WakeForest Imaging center for baseline MRI scan. Studies have shown that 5-6% of liver fat is considered normal and anything more than that can reflect increased risk for fatty liver. If the MRI report of the participants shows liver fat > 6%, we will consult with the participant (if > 18years) and/or their parents in confidence and explain why they (or their child) cannot continue to

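### The fallback of adding SNPs has no matching rule for the risk-allele cut-offs; if the stated counts are kept, the low-risk group can only shrink and no extension tried fills both groups

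*Combined protocol and SAP*

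**What the plan says.** Section 4.1 (Genotyping) expects to find the 48 participants among 200 people genotyped for the 10 SNPs in Table 1. It then gives a fallback for the case that individuals with those SNPs are not found: "we will mine the literature and find more SNPs that have a role in liver lipogenesis".

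Section 4.2 defines the score as an unweighted count of 0, 1 or 2 per SNP: "All the score will be added to get a cumulative score between 0 and 20 for 10 SNPs". It also sets the selection rule: "We will select participants having > 15 risk alleles and < 6 risk alleles for our acute challenge and 3-week intervention study". The Study Phases row of the synopsis uses the same strict limits. The Study Design row uses inclusive ones: "12 children and young adults with 15 or more risk alleles and 12 children and 12 young adults with 6 or fewer risk alleles".

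Four things are not stated:
- how the cut-offs change if the list grows
- how many SNPs may be added
- whether all 200 people are re-scored
- which allele of each Table 1 SNP is the risk allele (section 4.2 gives only the principle)

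**The concern.** High against low genetic risk is the study's only group contrast (section 3.2). Section 1.4 presents the fixed set as the novelty: "The only difference is that we are using a set of 10 genotypes instead of individual genotypes". Section 6.4 intends the data for sizing a larger study.

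A raw count with raw cut-offs has meaning only for a given list. A count of 15 is 75% of the 20 alleles on 10 SNPs, 50% of 30 alleles on 15 SNPs and 37.5% of 40 alleles on 20 SNPs. If the list grows and the counts do not move, group membership partly reflects how many SNPs were added. If the counts do move, the new ones would be chosen after the genotypes are known. Either way the protocol does not fix one definition of genetic risk in advance, and the fallback may not deliver the two groups it is meant to rescue.

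**Working it through.** **Inputs from the protocol.** Table 1 minor allele frequencies: 0.23, 0.45, 0.07, 0.39, 0.49, 0.07, 0.48, 0.42, 0.21, 0.07 (sum 2.88). 200 people genotyped. 24 needed per risk group, so 24/200 = 12% in each tail.

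**Assumptions, not in the protocol.** Hardy-Weinberg proportions; independent SNPs; added SNPs sharing one risk-allele frequency q. Because risk alleles are not listed, all 2^10 = 1,024 codings were run. The trigger wording is unclear and is read here as too few people meeting the cut-offs.

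**Method.** Each SNP with risk-allele frequency p contributes 0, 1 or 2 with probabilities (1−p)², 2p(1−p), p². Convolving these gives the exact distribution of the score. Its mean is the sum of 2p and its variance the sum of 2p(1−p). Expected numbers are 200 × tail probability.

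**Step 1: the plan's own figure, 24 + 24 of 200, before any extension.** The variance is 3.5336 (SD 1.88) under every coding.
- All minor alleles as risk: mean 2 × 2.88 = 5.76.
- All major alleles as risk: mean 20 − 5.76 = 14.24.
- Best-balanced coding (major allele as risk for EFCAB4B, NCAN, COL13A1, LYPLAL1 and PPP1R3B): mean 2 × (1.56 + 3.68) = 10.48.

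No coding gives 24 expected in both groups. The best is about 3 and 3, so the plan's figure is not reproduced and the fallback would very likely be needed.

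**Step 2: direction.** Let S be the 10-SNP score and A ≥ 0 the count from added SNPs. Then P(S + A ≥ 15) ≥ P(S ≥ 15) and P(S + A ≤ 6) ≤ P(S ≤ 6), for any frequencies. With fixed cut-offs the extension can never relieve a shortage in the low group.

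**Step 3: size.** Expected numbers of 200 with the cut-offs held:

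| Coding | Added SNPs | High (≥15) | Low (≤6) | High (>15) | Low (<6) |
|---|---|---|---|---|---|
| Balanced | none | 3.0 | 3.0 | 0.6 | 0.6 |
| Balanced | 3 at 0.3 | 31 | 0.6 | 14 | 0.1 |
| Balanced | 5 at 0.3 | 66 (33%) | 0.2 (0.09%) | 39 (20%) | 0.03 |
| All minor | none | 0.0007 | 132 | 0.00005 | 91 |
| All minor | 10 at 0.1 | 0.6 (0.3%) | 60 (30%) | 0.2 | 33 |
| All minor | 10 at 0.3 | 32 | 4.9 | 18 | 1.7 |
| All minor | 15 at 0.3 | 105 (53%) | 0.5 (0.25%) | 80 (40%) | 0.1 |
| All major | none | 91 | 0.007 | 51 | 0.0007 |

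Two rows by hand:
- Balanced, +5 at 0.3: mean 10.48 + 5 × 0.6 = 13.48; variance 3.5336 + 5 × 0.42 = 5.6336; SD 2.37. The cut-off of 15 falls from (15 − 10.48)/1.88 = 2.40 SD above the mean to (15 − 13.48)/2.37 = 0.64 SD.
- All minor, +10 at 0.1: mean 5.76 + 10 × 0.2 = 7.76; variance 3.5336 + 10 × 0.18 = 5.3336; SD 2.31. The cut-off is still (15 − 7.76)/2.31 = 3.13 SD above the mean.

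**Step 4: can any extension fill both groups?** All 1,024 codings were crossed with q from 0.01 to 0.93 and up to 150 added SNPs. With the inclusive cut-offs the smaller group peaks at 15.6 of 200, and that takes 116 SNPs at q = 0.02. For q from 0.07 to 0.50 the peak is 14.9. With the strict cut-offs the peak is about 7. None reaches 24.

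**The case against.** Several objections have force.

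- **Silence on the cut-offs.** A reader might infer that 15 and 6 will be kept on a longer list. The protocol does not say so. Section 4.2 ties the score to 10 SNPs ("The number of risk alleles will range from 0 to 20"), so the sponsor may intend new counts. What the text supports is that no rule is given, and that the only counts available fail if used.
- **How far the groups drift.** A reader might also infer that high risk comes to mean an average person and that the low group vanishes. That is not general. With all minor alleles as risk and 10 SNPs added at 0.1, 30% are still low and only 0.3% are high. With that coding and q = 0.288 (the Table 1 mean), the high group first reaches 24 expected at +10 SNPs. The cut-off is then still 1.26 SD above the mean, and about 6 of 200 are low. Half of people score 15 or more only from +16.
- **Yield of the 10-SNP score.** The more basic problem is that the cut-offs do not fit the Table 1 frequencies even with no SNP added. This stands. With all major alleles as risk, the low group is empty from the start and the fallback is not the cause. Correcting the cut-offs alone would still leave an open-ended extension in the protocol.
- **Different scores for early and late enrolees.** The documents do not support this reading. They describe genotyping 200 people and then selecting 48, and nothing describes rolling scoring.
- **Exploratory study.** The study disclaims power, and genotyping precedes the MRI and the challenge, so extending the list would not be driven by outcomes. Both are true, but neither supplies a single definition of the exposure.

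**Conclusion.** The concern holds in a conditional form. The protocol permits an open-ended extension of the SNP list with no rule for cut-offs, number of SNPs or re-scoring. If the stated counts are applied to a longer list, the direction of the shift is certain and needs no assumption about frequencies. Under Hardy-Weinberg and independence, no extension tried gives 24 high and 24 low from 200.

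The amount of drift is not a single figure. It runs from 33% high and 0.09% low (balanced coding, +5 at 0.3, inclusive cut-offs; 20% high with the strict one) to 0.3% high and 30% low (all minor, +10 at 0.1). Correlated SNPs or a sample enriched for risk alleles would change these numbers but not the direction. Because the rule alters the study's only group contrast after genotypes are known, it should be settled before genotyping starts.

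**What to change.** 1. Reconcile the cut-offs in the Study Design row, the Study Phases row and section 4.2, which now differ between strict and inclusive limits.
2. Add to Table 1 the risk allele of each SNP, and fix the list and the alleles before the first genotype is read.
3. Apply that one score to all 200 people.
4. Replace the fallback sentence in section 4.1 with selection by rank: the 12 highest and 12 lowest scores among children, and the same among young adults. State in advance how ties at the boundary are broken and that the next-ranked person replaces anyone found ineligible.
5. Report the distribution of scores actually enrolled in each cell.

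If the sponsor prefers a longer list, that can work too, provided the list is fixed before genotyping and the groups are set from the score's own distribution across all 200.

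The cost is protocol wording only. The downside is that the groups may be less extreme than 15 and 6 imply. With all minor alleles as risk, for example, only 7.5% (15 of 200) score 9 or more, so the top 24 would include some people scoring 8. The lowest 24 would come from the 26% (51 of 200) scoring 4 or less. Reporting the enrolled scores makes that contrast visible to whoever sizes the next study.

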Specific Aim3: Determine the relationship between markers of DNL, liver fat accumulation and serum concentrations of lipids, uric acid and liver function markers before and after the fructose challenge

- We will measure serum concentrations of liver function markers, lipids and uric acid at week 0 and week 3;
- As in previous aims, data will be analyzed using students T test, and Pearsons correlations.

Subject Population	Inclusion Criteria
key criteria for Inclusion and Exclusion:	
 Subjects between 12 and 40 years No history of alcohol abuse (> 7 drinks per week) History of fructose intake of < 14 drinks per week Caucasian ethnicity BMI > 25kg/m² – 32kg/m² or 85th -99th percentile but otherwise healthy
	Exclusion Criteria
	
 ages < 12 and > 40 years Pregnant/lactating known alcohol abuse or fructose intake > 14 drinks per week not of Caucasian ethnicity glucose levels > 100 mg/dl if fasting, > 140mg/dl if within 2 hours post meal and > 200 mg/dl if random sample taking anti-hypertensive, anti-diabetic, uric acid and/or lipid-lowering medications known diagnosis of diabetes, fructose intolerance, chronic kidney disease, NAFLD or any liver-related disease, hypertriglyceridemia, polycystic ovary syndrome, hypothyroidism, obstructive sleep apnea, hypopituitarism and hypogandism BMI < 25kg/m² or > 32 kg/m² or < 85th or > 99th percentile Liver fat fraction >5% as per baseline MRI scan
Number Of Subjects	200 for first phase and 48 for the second and third phases
Study Duration	The first phase will be about 30 minutes and the second and third phase will be divided into two visits. Both visits in both phases will be about 3.5 hours each.
Study Phases	(1) Screening: We will screen participants for eligibility to participate in the study based on the inclusionary/exclusionary criteria specified above. The 200 children and young adults selected to participate will provide saliva which will be used to extract DNA and then genotype 10 SNPs. These SNPs are selected based on their association with de novo lipogenesis (DNL) or liver fat accumulation in previously published studies in Caucasians. We will select 12 children and 12 young adults with more than 15 risk alleles and 12 children and 12 young adults with less than six number of risk alleles.
Screening	
Study Treatment	
Follow-Up	

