	(2) Intervention: This part is divided into two phases. Each phase entails two visits. Phase2-visit 1: The 48 enrolled (24 in each of the high and low genetic risk group) will

visit the UNC NRI clinical suite run by the Human Research Core. They will be taken to the WakeForest imaging center for their baseline MRS scan.

Visit 2: Acute fructose challenge: The next day, they will have their initial anthropometrics and Fibroscan measurements. They will then undergo an oral fructose challenge using a protocol used by Hudgins et al¹³. The participants will be provided with a drink consisting of fructose (0.75g/kg body weight) + glucose (0.45g/kg body weight) dissolved in 24 Oz of water (equal to 2 soda cans) to be consumed within 15 minutes. Blood and urine will be sampled at baseline and 1 and 3 hours after sugar drink ingestion. During the challenge period, no other beverage (except water) or food will be allowed.

3-week intervention: The 48 participants will be provided with sugar drinks for the three week period. The drinks that need to be taken per day will contain fructose (0.75g/kg body weight) + glucose (0.45g/kg body weight) dissolved in 24 Oz of water (equal to 2 soda cans) which is similar to that provided during the acute fructose challenge⁷.

[figure not shown]
Addition of glucose to fructose in the challenge and 3-week intervention induces the lipogenic effects of fructose, alleviates gastrointestinal effects of fructose and mimics the real-life situation¹⁴. They will visit at the end of each week to collect drinks for the next week. In addition, participants will be given standardized meals for the day prior to the baseline fructose challenge. They will also be instructed to avoid alcohol, juices and sodas the previous evening.

Efficacy Evaluations	Changes in liver fat accumulation through MRI scans and fibroscan measurements, and serum concentration of other lipids, liver function markers and uric acid.
Pharmacokinetic Evaluations	N/A

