Genes and gene by nutrient interactions play a major role in the regulation of NAFLD: Both genetic and environmental factors contribute to the onset and progression of NAFLD. NAFLD is a complex and heritable phenotype. Family-based studies have reported heritability estimates for NAFLD to be between 20% and 70%^{7,8}. Genome-wide and candidate gene studies have identified several genes associated with NAFLD⁸. Representative genes that were implicated in lipid metabolism and in the development and progression of NAFLD are shown in **Table1**. Few studies have shown that fructose affects lipogenesis in liver in a genotype-specific manner. Davis and colleagues found that Hispanic children with GG genotypes of *PNPLA3* SNP rs738409 were more inclined to accumulate fat in the liver as compared to children with CC or CG genotypes³. Similarly, another study investigating the effects of added sugars on liver fat found that individuals with TT of rs1260326 of *GCKR* increased their *de novo* lipogenesis by 44% during an oral fructose + glucose challenge⁴. However, none of the studies have shown the cumulative effects of SNPs on change in liver fat when exposed to fructose.

The genetic-specific effects of fructose on liver lipogenesis need to be studied as a first step towards individualized nutrition: This study assumes significance given that fructose affects liver lipogenesis differentially based on genotypes. It also paves the way towards individualized or personalized nutrition. Previous studies investigating the metabolic effects of fructose have been controversial. Some have shown significant effects of fructose on insulin sensitivity and *de novo* lipogenesis and triglycerides while others have shown no effects²³⁻²⁷. The range of these studies is wide, with the duration of the intervention ranging from 7 to 665 days, sample size ranging between 8 and 64 per group and amount of fructose per day ranging from 40 to 250g/d. For this exploratory and feasibility study we have selected the duration of 21 days, sample size as 12 per group and amount of fructose a ~0.75g/kg/day (equivalent to two sodas/per day).

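### At the Table 1 allele frequencies, neither version of the risk-allele cut-offs can be expected to yield 24 high-risk and 24 low-risk participants from 200 genotyped

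*Combined protocol and SAP*

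**What the plan says.** All references are to the combined protocol and SAP. The score is an unweighted count, 0, 1 or 2 per SNP, over ten SNPs (section 4.2).

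The cut-offs appear in two versions:

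- **Inclusive** (synopsis, Study Design): "with 15 or more risk alleles and 12 children and 12 young adults with 6 or fewer risk alleles".
- **Strict** (synopsis, Study Phases): "with more than 15 risk alleles and 12 children and 12 young adults with less than six number of risk alleles". Section 4.2 agrees: "We will select participants having > 15 risk alleles and < 6 risk alleles for our acute challenge and 3-week intervention study".

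The synopsis puts the 48 enrolled at "24 in each of the high and low genetic risk group". Section 1 gives "sample size as 12 per group".

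Feasibility is argued in section 4.1, Genotyping: "The minor allele frequencies (MAFs) of these SNPs range between 7 and 49% based on Caucasian ethnic background", followed by "Therefore we are confident about finding 48 individuals with all 10 SNPs". If that fails, "we will mine the literature and find more SNPs that have a role in liver lipogenesis". No score distribution is shown, and Table 1 does not say which allele of each SNP carries the risk.

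**The concern.** A sum of ten SNP counts clusters around its mean. Cut-offs 9 or 11 alleles apart on a 20-point scale can leave one or both tails almost empty. A range of minor allele frequencies says nothing about how many people fall in both tails.

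The study depends on having both groups. The hypothesis and primary objective are about genotype-specific effects of fructose, and Aims 1 and 2 in the synopsis plan unpaired t-tests between the two groups. The stated purpose is preliminary data for a larger study of these genotypes. If one group cannot be formed, that contrast is not estimated at all, which is a different problem from estimating it with low power.

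**Working it through.** **Inputs.** 200 genotyped (section 4.1); 24 needed per group (synopsis). Minor allele frequencies from Table 1: PNPLA3 0.23, GCKR 0.45, TM6SF2 0.07, APOC3 0.39, EFCAB4B 0.49, NCAN 0.07, COL13A1 0.48, FDFT1 0.42, LYPLAL1 0.21, PPP1R3B 0.07. The plan gives no calculation of its own to reproduce.

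**Assumptions.** Hardy-Weinberg proportions and independence between SNPs; the protocol states neither.

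**Spread.** With p the risk-allele frequency and q = 1 − p, each SNP contributes variance 2pq, whichever allele carries the risk. The sum of pq is 0.1771 + 0.2475 + 3 × 0.0651 + 0.2379 + 0.2499 + 0.2496 + 0.2436 + 0.1659 = 1.7668. So SD = √(2 × 1.7668) = √3.534 = 1.88. The inclusive cut-offs (15 and 6) are 9 alleles apart, or 9/1.88 = 4.8 SD. The strict ones (16 and 5) are 11 apart, or 5.9 SD.

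**Tails.** The exact score distribution is the convolution of ten Binomial(2, p) variables. Because risk alleles are not named, p was set to the MAF or 1 − MAF in all 2^10 = 1,024 combinations. Expected count = 200 × tail probability.

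| Quantity | Inclusive | Strict |
|---|---|---|
| Assignments with an expected 24 in both groups | 0 | 0 |
| Best expected count in the scarcer group | 3.02 | 0.62 |
| Chance of 12 or more there, Binomial(200) | 6.2e-5 | 2.9e-12 |
| Assignments where one group reaches an expected 24 | 331 | 127 |
| Largest count in the other group in those cases | 0.22 | 0.003 |

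The best assignment has mean score 10.48. A normal check on its upper tail gives (14.5 − 10.48)/1.88 = 2.14, tail probability 0.016 and about 3.2 per 200, close to the exact 3.02. Fixing PNPLA3 G and GCKR T as risk alleles, as the background suggests, leaves the best case unchanged.

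**Departure from Hardy-Weinberg.** With no heterozygotes at all, the extreme case, each SNP scores 0 or 2 and the variance doubles. The best scarcer group is then 12.4 (5.2 strict).

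**Adding SNPs with cut-offs kept (an assumption).** For any number of independent SNPs at any frequencies, both tails are bounded by those of a Poisson variable with the same mean. Maximising the smaller tail over the mean gives 21.3 per 200 at mean 10.41 (strict 11.6 at mean 10.25), still below 24. Added SNPs linked to the listed ones are outside this bound.

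The main counts ignore the 12 and 12 age split and the baseline MRI exclusion, both of which make the shortfall worse.

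**The case against.** The strongest reply is that this is an exploratory feasibility study that disclaims power (section 6.4). The shortfall would show at genotyping, before any scan or drink, when an amendment could still correct it. That limits the harm. It does not make the written plan workable, because low power is disclaimed but an empty group is not.

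A reader might infer more than the documents support on five points:

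- **The score could be tuned after liver-fat data are seen.** The monitoring plan has investigators review genotype and phenotype data as they arise, but it does not permit re-scoring. Sections 4.1 and 4.2 put genotyping and selection before MRI. The most that can be said is that the score is not expressly locked.
- **12 per group contradicts 24 per group.** Section 1 can be read as meaning each age-by-risk cell, and four cells of 12 make 48. It needs clarifying.
- **The protocol claims to find 48 people in the two tails.** The phrase about having all ten SNPs leaves that sentence unclear. What stands is that the MAF range does not support 24 and 24.
- **The fallback is bound to fail.** Adding SNPs changes the scale, and the protocol does not say whether the cut-offs would stay. The ceiling of 21.3 (11.6 strict) applies only if they do.
- **Only changes over time are analysed.** Section 6.3 stresses week 0 versus week 3, but it also plans a regression on AUC, and the synopsis plans between-group tests.

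**Conclusion.** The point holds. The cut-offs contradict each other on the page, which needs no assumption. Under Hardy-Weinberg proportions and independence, neither version yields both groups. The best scarcer group is about one eighth of the 24 needed (3.0) under the inclusive cut-offs and about one fortieth (0.6) under the strict ones. The result does not hinge on Hardy-Weinberg, since removing every heterozygote still gives only about half of what is needed. The fallback states no revised score range or cut-offs, so it cannot be relied on as written. This must be fixed before genotyping starts, because the primary objective cannot be addressed without a second group.

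**What to change.** 1. State one pair of cut-offs, or none, consistently in the synopsis (Study Design, Study Phases) and section 4.2. Clarify the 12 per group in section 1 as each age-by-risk cell, if that is intended.
2. Replace the fixed cut-offs with rank selection. Within each age stratum (state the age boundary), take the 12 highest and 12 lowest scores among eligible genotyped participants. Break ties at random, and let the next rank replace anyone excluded at baseline MRI.
3. Fix the SNP list and the risk allele of each SNP before any MRI. Drop the fallback or specify it fully.
4. Report the achieved allele counts per group.

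**Cost.** This is protocol wording only; 200 genotyped and 48 treated are unchanged. High and low become relative to the screened sample, and selection waits until a stratum is fully genotyped. The genetic contrast also shrinks from the nominal minimum gap of 9 or 11 alleles. The split of the 200 by age is not given, so simulated values are shown for a range (alleles; minimum gap within stratum, then mean difference):

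| People in stratum (assumed) | 12 per tail | 15 per tail (if MRI exclusions push selection to rank 15) |
|---|---|---|
| 60 | 3.3, 5.1 | 2.6, 4.7 |
| 100 | 4.5, 6.1 | 3.9, 5.7 |
| 140 | 5.2, 6.7 | 4.7, 6.3 |

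**Alternatives.** Pre-set cut-offs about 4 alleles apart are workable. With 100 per stratum they fill all four cells of 12 with probability 87–98% before MRI exclusions, whereas rank selection always fills them if each stratum is large enough. Keeping the present cut-offs and screening more people would take about 24 × 200/3.017 ≈ 1,590 genotyped (strict: 24 × 200/0.621 ≈ 7,730) for an expected 24 per group, even at the best assignment.
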